**Collaborators:**

[name]  
[name]  
[name], PhD  
[name]  
[name]

**Study Coordinator:** [name], CCRP

Division of Gastroenterology & Hepatology, Mayo Clinic Rochester, MN

Eosinophilic esophagitis is a relatively new disease in which esophageal eosinophilia leading to inflammation and stricture formation results from exposure to food antigens. Although it would seem logical that identification and removal of food antigens would be the definitive treatment, this is more easily said than done.

There are several reasons for this:

- Current available allergen testing, mostly through blood and skin, do not reliably reflect specific allergen sensitivity in the esophagus.
- As there has not been a non-invasive test to determine the esophageal response to single food allergens, clinicians have had to choose between allergen avoidance therapy because it is too cumbersome or performing serial and at times numerous endoscopies and biopsies to fully evaluate a range of potential foods that may trigger the inflammatory response.
- Treatment of eosinophilic esophagitis is also further hampered by a distinct lack of symptoms in adults due to what is typically a silent inflammatory response until stricture formation and subsequent dysphagia and impaction occur.
- Furthermore, adult patients with this disease typically accommodate by careful chewing and slow eating such that an absence of symptoms commonly underestimates the severity

of disease. As a result, an invasive test that reliably determines esophageal eosinophilic would be extremely valuable for monitoring disease activity and the response to food allergen withdrawal or introduction.

Cytosponge is an ingestible gelatin capsule containing a compressed mesh attached to a string. The capsule is swallowed and once in the stomach, the gelatin dissolves and a spherical mesh of 3 cm diameter is released. The mesh is withdrawn through the mouth by the attached string and a cytologic specimen is collected.

Current cytosponge from University of Cambridge

Covidien Cytosponge

In a recent study evaluating the Cytosponge in patients with Barrett's esophagus, excellent results were achieved with a the sensitivity and specificity of the test was 73.3% (95% confidence interval 44.9% to 92.2%) and 93.8% (91.3% to 95.8%) for 1 cm or more circumferential length and 90.0% (55.5% to 99.7%) and 93.5% (90.9% to 95.5%) for clinically relevant segments of 2 cm or more.

There was also overall excellent tolerance by patients using the Cytosponge. As a result, one might wonder if the Cytosponge would similarly be a reliable relatively non-invasive tool for evaluating patients with eosinophilic esophagitis.

**Specific Aim:** To evaluate the sensitivity and specificity of Cytosponge when compared to upper endoscopy and biopsies/swab testing in patients undergoing clinically indicated endoscopy for evaluation of eosinophilic esophagitis and healthy controls

### **Methods:**

- Patients with eosinophilic esophagitis and health controls, (patients without esophageal symptoms such as GERD or dysphagia), will be enrolled.
- Patients with EoE will be having a clinically indicated upper endoscopy and biopsies either for initial diagnosis or for monitoring the activity of their disease.
- All patients will be asked to be fast, no solid food 8 hours prior to swallowing the cytosponge, can drink clear liquids up to 2 hours prior to swallowing the cytosponge
- The EoE subjects two hours prior to endoscopy will be asked to swallow the Cytosponge. Briefly, the capsule and bunched up string are swallowed with water. Two hours is chosen as the time interval because water will likely be needed to swallow the capsule and this is the standard time allowed for to last safely consume a clear liquid prior to endoscopy.
- Controls will be will have the same fasting instructions but will not be required to be having and endoscopy.
- The string is held without any tension to allow the capsule to move into the stomach. The patient holds onto the string for five minutes after ingestion to allow the capsule to dissolve in the proximal stomach, where a spherical mesh of 3 cm diameter is released.
- The back of the throat is then sprayed with 1% lidocaine and the expanded mesh withdrawn by pulling on the string with the patient's head in an extended position.
- After retrieval the string is cut and the Cytosponge containing the cytological specimen placed in preservative fluid and kept at room temperature until transportation to the laboratory.
- The whole process of administering the Cytosponge, including instructing the patient, takes less than 10 minutes.
- Following this, the clinically indicated endoscopy will be performed. The cytology specimens will be reviewed by one pathologist who will read them blindly without knowledge of the results of the biopsy specimens. The cytology specimens will be

compared to the biopsy in terms of esophageal eosinophil presence and density. A scoring system for cytology will be devised.

- Samples from the University of North Carolina will be sent to the Mayo Clinic to be reviewed by the same pathologist.
- After the Mayo pathologist have completed their analysis, slides and part of the uncut blocks will be sent to [name] lab at the University of Cambridge looking at reproducibility of results, evaluation of the mucosal microbiome by sequencing and additional biomarker studies including RNA, methylation and protein analyses.
- We will send samples from a cell block made from the cytology fluid from the cytosponge and a portion of the primary cytosponge placed in RNAlater solution for extra-cellular RNA signature analysis with possible detection of EoE specific lumen protein products proposed to [name] lab at the University of Cincinnati.
- FFPE RNA from the concurrent biopsies at the time of the EGD if available as biopsy tissue represents the source of the dislodged cells/tissue pieces by the cytosponge. Parallel comparison will provide key clue to validate the new diagnostic approach.
- We will stain sections from esophageal biopsies and Cytosponge for the eosinophil secondary granule protein eosinophil peroxidase (EPX). This may increase the diagnostic sensitivity of the Cytosponge because EPX staining accounts for eosinophil degranulation products in addition to intact eosinophils. H+E stains and their matching EPX stains will be digitized using an Aperio slide scanner and Aperio ImageScope software will be used for quantification of EPX.
- Modification 11/24/2021 – we would also like to utilize slides from IRB15-004741 on patients that had a cytosponge and biopsy. These will undergo the EPX staining as described above. Possible samples used will be cross checked in Ptrax to ensure the subjects consented to allowing their samples to be utilized in future research and only the applicable samples will be used. Total Mayo participants to use from this study will be up to 30.

**Recruitment:** We will recruit 130 participants at Mayo there will be 180 total subjects in this trial

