**Inclusion Criteria:**

- Adult patients between the ages of 18 and 65 with eosinophilic esophagitis or health controls including lactating or pregnant women undergoing clinically indicated endoscopy and esophageal biopsy.

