**Study flow:**

- The study coordinator will look for patients being seen in Esophageal clinic with the indication of EoE or healthy controls (patients without esophageal symptoms such as GERD or dysphagia)
- When the physician has an EoE patient scheduled for a clinically indicated upper endoscopy, to diagnose or monitor their disease, these patients will be approached by the study coordinator to see if they are interested in the cytosponge study?
- Subjects willing to swallow the cytosponge that do not have esophageal symptoms will be approached by the study coordinator.
- Patients with EoE will then be scheduled to come to Gonda 9s two hours prior to the endoscopy. Healthy controls will be scheduled to come to Gonda 9 at their convenience as long as they adhere to the fasting instructions.
- The physician will have the patient swallow the Cytosponge.
- The patient holds onto the string for five minutes after ingestion to allow the capsule to dissolve in the proximal stomach, where a spherical mesh of 3 cm diameter is released.
- The back of the throat is then sprayed with 1% lidocaine and the expanded mesh withdrawn by pulling on the string with the patient's head in an extended position.
- After retrieval the string is cut and the Cytosponge containing the cytological specimen placed in preservative fluid and kept at room temperature until transportation to the laboratory.
- The whole process will take approximately 10 minutes.
- A throat swab for collection will also be performed at this time to be processed for bacterial population of the esophageal mucosa.
- Following this, the clinically indicated endoscopy will be performed. Prior to biopsies we will do a brushing of the esophagus.
- The cytology specimens will be reviewed by one Mayo pathologist who will read them blindly without knowledge of the results of the biopsy specimens.
- The cytology specimens will be compared to the biopsy in terms of esophageal eosinophil presence and density. A scoring system for cytology will be devised.
- We will do further EoE/allergy analysis with FFPE slides including EDN and tryptase staining.
- When the Mayo pathologist have completed their analysis, slides and part of the uncut blocks will be sent to [name] lab looking at reproducibility of results, evaluation of the mucosal microbiome by sequencing and additional biomarker studies including RNA, methylation and protein analyses.

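### The cytology reader is masked to biopsy results only, so EoE or control status is not withheld, and for a control without a biopsy the rule masks nothing

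*Protocol*

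**What the plan says.** The Specific Aim is "To evaluate the sensitivity and specificity of Cytosponge when compared to upper endoscopy and biopsies/swab testing", in EoE patients and healthy controls.

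Methods gives the cytology reading to one pathologist "who will read them blindly without knowledge of the results of the biopsy specimens". Study flow repeats the rule with the same scope: "The cytology specimens will be reviewed by one Mayo pathologist who will read them blindly without knowledge of the results of the biopsy specimens". Specimens from the second center go to that reader as well: "Samples from the University of North Carolina will be sent to the Mayo Clinic to be reviewed by the same pathologist".

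On controls, Methods says they "will not be required to be having and endoscopy", and Study flow says "Healthy controls will be scheduled to come to Gonda 9 at their convenience as long as they adhere to the fasting instructions". Inclusion Criteria, however, speaks of "health controls including lactating or pregnant women undergoing clinically indicated endoscopy and esophageal biopsy", which can be taken to make endoscopy and biopsy a condition for controls too.

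Methods and Data Analysis both leave the cytology score to be devised, and no positivity cut-off is given. Methods also states that EoE patients may be having endoscopy for initial diagnosis or to monitor disease activity.

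**The concern.** Cytology is the index test. If its reader knows who is a patient and who is a healthy volunteer, doubtful slides may be called in the expected direction. Withholding the biopsy result guards against this only where a biopsy exists, and even there it does not hide group. The exposure is greater here because one person reads every slide with a score that has no stated cut-off.

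What is at stake is the pair of accuracy figures the study exists to produce. Analysis cannot undo a reading made with group known. For that reason the matter belongs in the Protocol's conduct rules and cannot be left to an analysis plan.

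**Working it through.** The Protocol gives no figure to reproduce on this point. It has no target accuracy and no EoE/control split, only 130 participants at Mayo and 180 in total (Recruitment).

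**1. What the stated rule withholds**

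| Specimen from | Biopsy result | EoE/control status | Clinical history, endoscopic findings |
|---|---|---|---|
| EoE patient | withheld | not addressed | not addressed |
| Control with biopsy (one reading of Inclusion Criteria) | withheld | not addressed | not addressed |
| Control without endoscopy (Methods, Study flow) | none exists | not addressed | not addressed |

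A reader could keep to the rule exactly and still know the group of every slide. Nothing in the Protocol calls for coded specimens or a mixed reading order.

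**2. Direction if group is known**

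- Biopsy-active EoE: some misses become positives, so sensitivity rises.
- Controls: some false positives become negatives, so specificity among controls rises.
- Biopsy-inactive EoE under monitoring: some true negatives are over-read as positive, so specificity in that subgroup falls.

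**3. Size, as an assumed illustration**

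Assumptions, none from the Protocol: true sensitivity se = 0.80; true specificity sp = 0.90; a share q of would-be errors is corrected.

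- Sensitivity = se + q(1 − se) = 0.80 + 0.20q
- Control specificity C = sp + q(1 − sp) = 0.90 + 0.10q

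| q | Sensitivity | Control specificity |
|---|---|---|
| 0.10 | 0.82 | 0.91 |
| 0.25 | 0.85 | 0.925 |
| 0.50 | 0.90 | 0.95 |

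With the Barrett's figures quoted in the Protocol's introduction (73.3% and 93.8%) as placeholders, q from 0.10 to 0.50 gives sensitivity 76.0% to 86.7% and control specificity 94.4% to 96.9%.

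**4. Pooled specificity**

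Let u be the assumed share of true negatives over-read in biopsy-inactive EoE, so that specificity there is I = sp(1 − u). With sp = 0.90, I = 0.855 for u = 0.05 and 0.81 for u = 0.10. Let w be the share of controls among non-diseased subjects.

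- Pooled specificity = wC + (1 − w)I
- It equals the true value at w = (sp − I)/(C − I), and is inflated only above that share.

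Results for sp = 0.90:

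- q = 0.25, u = 0.05: 0.045/0.070 = 0.64
- q = 0.50, u = 0.05: 0.045/0.095 = 0.47 (lowest)
- q = 0.10, u = 0.10: 0.090/0.100 = 0.90 (highest)

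With the Barrett's placeholders the break-even share runs from 60% to 94%. Starting from 75% and 85% it runs from 36% to 85%. The Protocol does not state w, so the sign of the pooled effect is open.

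**5. Against random error**

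Assuming 90 per group (180 split equally, which the Protocol does not say), the Clopper-Pearson 95% limits are:

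- 72/90 = 0.80: 0.702 to 0.877, arms of 9.8 and 7.7 points
- 81/90 = 0.90: 0.819 to 0.953, arms of 8.1 and 5.3 points

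At q = 0.50 the shifts are 10 and 5 points. At q = 0.10 they are 2 and 1 points.

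**The case against.** The strongest reply is that silence is not permission. The Protocol never says the reader is told the group, and blind reading may have been meant broadly. This stands in part. A reader might infer that the pathologist is in fact unmasked to group, and the document does not show that. What it shows is that such masking is not secured.

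Three other inferences go too far:

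- **That both accuracy measures would be inflated.** The Specific Aim takes endoscopy and biopsy as the comparator, and patients under monitoring may be biopsy-inactive. For them group knowledge works against specificity. Within the EoE group, the existing rule does hide who is active.
- **That site gives group away.** Study flow sends both EoE patients and controls to Gonda 9. No group split by site is stated, and nothing ties the second center to patients only.
- **That the bias could match the confidence interval.** Under the assumed 90 per group the intervals are 17.5 and 13.4 points wide. Only sensitivity, at the extreme q = 0.50, reaches about one arm.

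It is also fair to say that controls may have biopsies, since Inclusion Criteria can be read that way. That conflict needs resolving, but a biopsied control could equally be read with group known.

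Finally, the Protocol plans a reproducibility review in Cambridge and a pixel-count algorithm for EPX. The first follows the Mayo reading and has no stated masking to group. The second does not mask the cytology reading.

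**Conclusion.** The point holds as a masking rule drawn too narrowly for the stated aim. It covers biopsy results only, gives no protection for a control without a biopsy, and leaves EoE/control status unmasked in text. Group knowledge would tend to raise sensitivity and specificity among controls, and may lower specificity among biopsy-inactive EoE patients. The direction for pooled specificity depends on a case mix that is not given.

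The size cannot be derived from the document. The 82% to 90% and 91% to 95% in the illustration rest wholly on the assumed 80% and 90% starting values and on 10% to 50% of errors being corrected. Actual practice may already be better than the text. This is a worthwhile, inexpensive correction and does not show that the results are biased.

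**What to change.** - Amend the masking sentence in both Methods and Study flow so that cytology is read without knowledge of biopsy result, EoE/control status, clinical history or endoscopic findings.
- Label every sponge specimen with a study code only.
- Read EoE and control specimens from both centers in mixed random order.
- Fix the cytology score and its positivity cut-off before the masked reading starts.
- Reconcile Inclusion Criteria with Methods and Study flow on whether controls have endoscopy and biopsy.

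The cost is some relabelling by the coordinator and a short wait while mixed batches are assembled. No extra reader and no further patient procedure is needed.

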**Inclusion Criteria:**

- Adult patients between the ages of 18 and 65 with eosinophilic esophagitis or health controls including lactating or pregnant women undergoing clinically indicated endoscopy and esophageal biopsy.

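### The inclusion criterion requires eosinophilic esophagitis, but the aim, Methods and Study flow enrol patients at initial diagnosis; the status of suspects whose biopsy is negative is left undefined

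*Protocol*

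**What the plan says.** Four places in the protocol describe who enters the patient group.

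- **Inclusion Criteria:** "Adult patients between the ages of 18 and 65 with eosinophilic esophagitis or health controls". The disease is stated as present, and no suspected category is given.
- **Specific Aim:** the population is "patients undergoing clinically indicated endoscopy for evaluation of eosinophilic esophagitis and healthy controls". The sponge's diagnostic accuracy (sensitivity and specificity) is to be judged there against endoscopy with biopsy or swab.
- **Methods:** patients with the disease have "clinically indicated upper endoscopy and biopsies either for initial diagnosis or for monitoring the activity of their disease". The sponge is swallowed two hours before the endoscopy. Controls do not have to have an endoscopy.
- **Study flow:** the coordinator screens for "patients being seen in Esophageal clinic with the indication of EoE or healthy controls", then approaches the "EoE patient scheduled for a clinically indicated upper endoscopy, to diagnose or monitor their disease".

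Recruitment gives 130 participants at Mayo and 180 in total. It does not divide them into patients and controls, or into first diagnosis and monitoring.

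**The concern.** A person having a first diagnostic endoscopy does not yet have the diagnosis. Because the sponge precedes the biopsy, nobody can say at enrolment whether that person meets a criterion that requires the disease. Whether it is met depends on the biopsy, which is part of the reference standard in the aim.

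Specificity is at stake. A suspected patient with a negative biopsy is a verified negative from the diagnostic part of the population the aim names, and a false-positive sponge matters most in such people. If they are kept out, or removed after a negative biopsy, the sample is selected on the reference result. The comparison then moves towards confirmed cases against symptom-free volunteers, where specificity tends to look better than it would in the clinic (spectrum bias).

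A later analysis plan could not fully repair this, since it cannot recover patients who were never enrolled. Data Collection describes two centres pooling their data, and each could read the sentence differently.

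**Working it through.** The protocol derives no figure on this point, and nothing behind the 180 can be reproduced. The only arithmetic it allows is 180 − 130 = 50 participants outside Mayo. The check is mainly one of consistency.

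**1. The passages side by side**

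| Section | Who is in the patient group | Suspects included? |
|---|---|---|
| Inclusion Criteria | Adults with the disease | Not if read literally |
| Specific Aim | Patients having endoscopy to evaluate the disease | Yes |
| Methods | Endoscopy for first diagnosis or monitoring | Yes |
| Study flow | Screened on the indication; endoscopy to diagnose or monitor | Yes |

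**2. Possible readings for a patient at first diagnosis**

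- (a) Not enrolled, because the disease is not established. This contradicts the other three sections.
- (b) Enrolled, then removed if the biopsy is negative. Eligibility then depends on the reference result.
- (c) Enrolled, biopsied and kept whatever the result. This fits the other three sections but not the literal criterion.

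The protocol does not choose between them.

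**3. Where negatives can come from**

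- Healthy controls: no endoscopy required under Methods, so largely unverified.
- Monitored patients with inactive biopsies: verified, and they meet the criterion literally. They count as negatives because Methods and Study flow compare sponge and biopsy on the presence and density of eosinophils, not on the diagnostic label.
- Suspects with a negative biopsy: verified, and lost under (a) or (b).

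**4. Illustration of scale (every input is assumed)**

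Let N be the number of endoscoped patients, s the share at first diagnosis, q the share of those with a negative biopsy, and r the share of monitored patients with an inactive biopsy.

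- Negative suspects = N × s × q
- Inactive monitored patients = N × (1 − s) × r
- Share of verified negatives lost = negative suspects ÷ (negative suspects + inactive monitored patients)

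The ranges tried were N = 90, 120, 150; s = 0.2, 0.5; q = 0.3, 0.6; r = 0.2, 0.4. Counts are rounded to whole patients.

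- Smallest loss, N = 90, s = 0.2, q = 0.3, r = 0.4: 90 × 0.2 × 0.3 = 5.4, so 5; 90 × 0.8 × 0.4 = 28.8, so 29; 5 ÷ 34 = 15%.
- Largest loss, N = 90, s = 0.5, q = 0.6, r = 0.2: 90 × 0.5 × 0.6 = 27; 90 × 0.5 × 0.2 = 9; 27 ÷ 36 = 75%.
- Example, N = 120, s = 0.5, q = 0.3, r = 0.2: 120 × 0.5 × 0.3 = 18; 120 × 0.5 × 0.2 = 12; 18 ÷ 30 = 60%.

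Exact (Clopper-Pearson) 95% intervals for the example, at an observed specificity of about 0.90:

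- All 30 verified negatives, 27 of 30 correct: 0.74 to 0.98.
- The 12 that remain without the suspects, 11 of 12 correct: 0.62 to 1.00.

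No scenario reached zero. The fewest verified negatives left was 9 and the most 48.

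**The case against.** The best defence is that this is loose wording. Methods and Study flow apply the disease label to people whose endoscopy is diagnostic, and Study flow screens on the indication. In the protocol's own usage the label may cover suspects, and the criterion can be read the same way. No section contains a rule for exclusion, withdrawal or replacement after biopsy. This stands as far as it goes: removal is a possibility, not a stated design. It does not remove the defect, because an undefined status allows the decision to be taken after the biopsy is known.

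Three stronger readings are tempting, and the document does not support them.

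- *Biopsy-negative suspects are dropped.* A reader might infer this, but the protocol never says so.
- *Specificity loses its verified negatives.* Monitored patients with inactive biopsies remain. The lack of verification in controls comes from the control rule in Methods, not from this criterion. The endoscopy clause that ends the inclusion sentence can even be read as covering controls, which is a separate conflict.
- *Specificity is overstated by 8 to 28 points.* That range appears if one assumes 98% in controls and 70% to 90% in biopsy-negative patients, but it is only one assumption taken from another (98 − 90 = 8; 98 − 70 = 28). It is also wrong to treat all biopsy-negative patients as lost, since the criterion does not touch monitored ones.

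It is also fair to say that the choice of main specificity figure may sit in an analysis plan not shown, and that the aim expressly includes healthy controls.

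**Conclusion.** The point holds as a contradiction within the protocol: the criterion conflicts with the aim, Methods and Study flow, and cannot be verified at enrolment for patients at first diagnosis. The consequence is a risk of spectrum and selection bias in specificity through losing an important part of the verified negatives.

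The contradiction itself rests on no assumption. Its size does, and cannot be computed from the protocol. The 15% to 75% loss shows only that the effect could be small or large, depending on how many patients are at first diagnosis and how many biopsies are negative. The size of any bias in the specificity estimate is unknown. Severity: should-fix.

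**What to change.** - Reconcile the Inclusion Criteria with the Specific Aim, Methods and Study flow by admitting adults aged 18 to 65 with known or suspected eosinophilic esophagitis who are having a clinically indicated endoscopy with biopsy, or healthy controls.
- State that every enrolled patient who is biopsied stays in the analysis and is classified by that day's biopsy, not by the label at enrolment. Biopsy-negative patients are kept as reference-negative.
- Report specificity in biopsy-verified negatives separately from specificity in healthy controls without endoscopy. Which of the two is the main figure is the sponsor's choice, since the aim includes both groups.

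The text change is one eligibility sentence and two analysis sentences, with no added procedure. The price is a specificity in verified negatives that will probably be less favourable and less precise than one dominated by controls. As a guide, with assumed counts, 16 of 18 correct gives an exact 95% interval of 0.65 to 0.99, and 32 of 36 gives 0.74 to 0.97. If the sponsor wants tighter precision in that group, more endoscoped patients could be needed.
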